2.7.1 Adverse events (AEs)

Adverse event data will be summarized and presented using primary MedDRA system organ classes (SOCs) and preferred terms (PTs) according to the version of the MedDRA coding dictionary used for the study at the time of database lock. The actual version of the MedDRA coding dictionary used will be noted in the clinical study report. The system organ classes will be presented in alphabetical order and the preferred terms will be presented by descending count within each system organ class.

Summary tables by SOC and PT will be provided for

- Number (%) of participants with treatment-emergent AEs
- Number (%) of participants with treatment-emergent AEs by severity
- Number (%) of participants with treatment-emergent SAEs
- Number (%) of participants with treatment-emergent AEs leading to discontinuation
- Number (%) of participants with treatment-emergent AEs leading to death
- Number (%) of participants with drug-related AEs
- Number (%) of participants with drug-related SAEs
- Number (%) of participants with non-serious treatment-emergent AEs.

For all adverse event summaries, the number of treatment-emergent adverse events, the number and percentage of participants experiencing treatment-emergent adverse events and the time-adjusted rate of occurrence will be tabulated according to SOC and PT. Participants reporting more than one adverse event for a given PT will be counted only once for that term (most severe incident for the severity tables and most related incident for the relationship tables). Participants reporting more than one adverse event within a SOC will be counted only once for that SOC. Participants reporting more than one adverse event will be counted only once in the overall total. Rates of occurrence are adjusted by the sum of follow-up time across all participants, which is the time at risk from dosing to the start of first occurrence of event in those with event and to the end of follow-up, or data cutoff date, in those without the event.

An overview of adverse events will be presented consisting of the number and percentage of participants experiencing at least one event for the following adverse event categories:

- Any treatment-emergent adverse event;
- Any treatment-emergent adverse event “related” to OAV101;
- Any severe treatment-emergent adverse events;
- Any serious treatment-emergent adverse events;
- Serious treatment-emergent adverse events “related” to OAV101;
- Treatment-emergent adverse events leading to discontinuation of participant from study;
- Treatment-emergent adverse events leading to death;
- Treatment-emergent adverse events of special interest (cp. Section 2.7.1.1).

AEs and SAEs are primary endpoints. For details, see Section 2.5.

2.7.1.1.1 Adverse events of special interest / grouping of AEs

On the basis of important identified and important potential risks associated with OAV101, AEs of special interest (AESI) are identified by using Standard MedDRA queries (SMQ) with terms as follows:

Hepatotoxicity as hepatic disorders (SMQ), thrombocytopenia as transient thrombocytopenia (CMQ), dorsal root ganglia toxicity as DRG cell inflammation (CMQ), and cardiac events as ischemic heart disease (SMQ) or cardiomyopathy (SMQ) or cardiac arrhythmias (SMQ) or embolic and thrombotic events (SMQ) or myocardial infarction (SMQ), respectively.

Thrombotic microangiopathy is identified via the following approach:

- Criteria #1: cases with any one of the following PTs: thrombotic microangiopathy OR haemolytic uraemic syndrome OR atypical haemolytic uraemic syndrome.
- Criteria #2: cases with at least one PT from EACH of the following SMQs representing thrombocytopenia, hemolysis and relevant renal events respectively:
 - Haematopoietic thrombocytopenia (SMQ)
 - Haemolytic disorders (SMQ)
 - Acute renal failure (SMQ) OR Renovascular disorders (SMQ)

Summary tables for AESIs, will include severe AESIs, serious AESIs, and drug-related AESIs. All AESIs will be listed together with a summary of prednisolone equivalent dose regimens over time with study days of start and end of AESI and per dose of prednisolone equivalent indicated. The total number of days with prednisolone equivalent dosing will be derived.

2.7.2 Deaths

Deaths will be presented in data listings and summary tables as AEs with fatal outcome. All data will be considered for analysis up to the time of death.

See Section 2.6 on how composite strategy is used to consider death for development milestone achievements.

2.7.3 Laboratory data

Safety laboratory data generated by the central laboratory will be used in all analyses. Safety laboratory data generated by local lab will only be listed. In data listings, per parameter, values will also be given as multiples of upper normal range limits.

Laboratory parameters include hematology, chemistry and urinalysis variables.

Changes in selected safety laboratory variables are primary endpoints. For details, see Section 2.5.

Hematology variables include: hematocrit, hemoglobin, red blood cell (RBC) count, white blood cell (WBC) count, differential blood count (in measured values and % of WBC; neutrophils, lymphocytes, monocytes, eosinophils, basophils, bands), mean corpuscular volume

(MCV), mean corpuscular hemoglobin (MCH), mean cell hemoglobin concentration (MCHC), and platelets.

Chemistry variables include: ALT, ALP, AST, blood urea nitrogen (BUN), calcium, creatinine, gamma glutamyl transferase, glucose, serum total bilirubin, direct bilirubin, indirect bilirubin, total creatine kinase (CK), chloride, phosphorus, sodium, potassium, lactate dehydrogenase (LDH), GLDH, troponin-I, and bicarbonate.

Urinalysis variables include: specific gravity, pH, ketones, glucose, protein, blood, leukocyte esterase, nitrites, bilirubin, RBC count, WBC count, yeast, squamous epithelial cells, casts, crystals, bacteria.

Clinical laboratory test results will be summarized at each visit including End of Study/Early Termination, for minimum, maximum and final post-baseline values. Urinalysis variables will only be listed.

Laboratory data values will be categorized as low, normal, or high, based on normal ranges of the laboratory used in this study. Shift tables from baseline to minimum value, maximum value, and final values will be created. The shift tables will cross tabulate the frequency of participants with baseline values below/within/above the normal range versus minimum/maximum/final values below/within/above the normal range.

The number and percentage of participants meeting the criteria for ALT and bilirubin defined in Table 16-1 of the protocol will be summarized by weight bracket and overall including potential Hy's Law cases. Potential Hy's Law cases will be presented for maximum post-baseline values as combined, even if criteria are fulfilled at different times during the follow-up.

A participant or event will be counted if the post-baseline laboratory values meet the above criteria regardless of the baseline laboratory value (i.e., the post-baseline laboratory value does not need to be worse than the baseline laboratory value). For participants meeting any elevation criterion, a corresponding listing of all ALT, AST, alkaline phosphatase, INR, GLDH, and total, direct, and indirect bilirubin values will be provided.

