
^X Assessment to be recorded in the clinical database or received electronically from a vendor
 
¹ If discontinuation, all efforts should be made to complete the EOS assessments prior to study discontinuation.
 
² S = assessment to be recorded in source documentation only
 
³ complete white blood count with differential
 
⁴ Hematology assessment at Day 2 should be performed locally before discharge of the patients; further, platelets should be closely monitored following the first week after infusion.
 
⁵ Hematology assessments at Week 4 and Week 10 are only applicable for Germany
 
⁶ HIV antibody, Hepatitis C antibody, Hepatitis B surface antigen (HBsAG)
 
█
 
█
 
⁹ HFMSE and RULM will not be administered until patient reaches 24 months of age
 
¹⁰ physical assessments may occur over the span of more than 1 day within the visit window, but must not exceed 4 days
 
█
																	

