8.4 Safety

Safety assessments are specified below with the assessment schedule detailing when each assessment is to be performed ([Table 8-1](#)).

Safety parameters include demographics/medical history, physical and neurological examinations, vital signs, height and weight measurements, 12-lead ECGs, echocardiograms, laboratory assessments, and AE monitoring.

For details on AE collection and reporting, refer to [Section 10.1](#).

As per [Section 4.7](#), during a Public Health emergency as declared by Local or Regional authorities i.e. pandemic, epidemic or natural disaster, that limits or prevents on-site study visits, regular phone or virtual calls can occur based on the [Table 8-1](#) assessment schedule for safety monitoring and discussion of the participant's health status until it is safe for the participant to visit the site again.

If participants cannot visit the site for safety lab assessments through central labs, local lab collection may be used and results will be entered in the eCRF.

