8.4.1 Laboratory evaluations

A central laboratory will be used for analysis of all specimens collected. Details on the collections, shipment of samples and reporting of results by the central laboratory are provided to Investigators in the laboratory manual.

Safety samples that can be collected remotely will be collected and analyzed in line with the study laboratory manual. Where samples are collected and analyzed at a local laboratory instead of the central laboratory, Novartis will ensure the results reported are equivalent to central laboratory collection and analysis.

If participants cannot visit the site for safety lab assessments conducted through central labs, local lab collection may be used during a Public Health emergency as declared by Local or Regional authorities i.e. pandemic, epidemic or natural disaster, that limits or prevents on-site study visits.

If participants cannot visit the site for protocol specified safety lab assessments, an alternative lab (local) collection site may be used.

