8.4.1.1 Hematology

Hematology analysis will include a complete blood count with differential and platelet count. Samples will be collected and shipped in accordance with the laboratory manual provided by the central laboratory. Blood samples for hematology analysis will be collected as specified in the [Table 8-1](#).

Hematology analysis will include the following:

- Hematocrit
- Hemoglobin
- MCH
- MCHC
- MCV
- Platelets
- Red blood cells
- White blood cells
- Differential (Basophils, Eosinophils, Lymphocytes, Monocytes, Neutrophils, Bands)

To monitor platelet counts, hematology analyses required during in-patient dosing, as determined by the Investigator, and on Day 2 prior to discharge, will be performed as per investigational site standard procedures at the local laboratory. Investigators will receive hematology results from all other study visits from the central laboratory. Further, platelet counts should be closely monitored in the week following infusion and on a regular basis afterwards.

In the event that clinically significant and/or moderate or severe thrombocytopenia and anemia are noted, further evaluation to diagnose Thrombotic Microangiopathy (TMA) should be conducted in accordance of standard of care. If a clinical diagnosis of TMA is made, a complete complement panel should be obtained per standard of care.

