Conditions that were already present at the time of informed consent should be recorded in medical history of the participant.

Adverse events (including lab abnormalities that constitute AEs) should be described using a diagnosis whenever possible, rather than individual underlying signs and symptoms.

Adverse event monitoring should be continued until end of study.

Once an AE is detected, it must be followed until its resolution or until it is judged to be permanent (e.g., continuing at the end of the study), and assessment must be made at each visit (or more frequently, if necessary) of any changes in severity, the suspected relationship to the interventions required to treat it, and the outcome.

Information about adverse drug reactions for the investigational drug can be found in the Investigator's Brochure (IB).

Abnormal laboratory values or test results constitute adverse events only if they fulfill at least one of the following criteria:

- they induce clinical signs or symptoms
- they are considered clinically significant
- they require therapy

Clinically significant abnormal laboratory values or test results must be identified through a review of values outside of normal ranges/clinically notable ranges, significant changes from baseline or the previous visit, or values which are considered to be non-typical in participant with the underlying disease.

On the basis of important identified and potential risks associated with OAV101, AESIs are determined and categorized as follows. These will be summarized based on Standardized MedDRA terminology:

- Hepatotoxicity
- Thrombocytopenia
- Cardiac adverse events
- Dorsal root ganglia toxicity
- Thrombotic microangiopathy

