10.2 Additional Safety Monitoring

10.2.1 Liver safety monitoring

To ensure participant safety and enhance reliability in determining the hepatotoxic potential of OAV101, a standardized process for identification, monitoring and evaluation of liver events has to be followed.

Please refer to [Table 16-1](#) in Appendix 16.1 for complete definition and management of liver laboratory abnormalities.

[Table 16-1](#) should be followed up by the Investigator or designated personnel at the trial site, as summarized below.

If elevated, repeated liver chemistry tests (i.e. ALT, AST, TBIL, Fractionated BIL, INR, and GLDH) will be performed within 48-72 hours to confirm elevation. If results will not be available from the central laboratory, then repeated testing should be performed at a local laboratory to monitor the safety of the participant. If a liver event is subsequently reported, any local liver chemistry tests previously conducted that are associated with this event should have results recorded on the appropriate eCRF page. If liver function tests are elevated, follow-up requirements include (refer to [Table 16-2](#) and [Table 16-3](#)):

- Hospitalization of the participant, if appropriate
- Causality assessment of the liver event
- Thorough investigation and follow-up of the liver event, which may include, based on Investigator's discretion: serology tests, laboratory tests for other causes of hepatitis, including viral hepatitis, imaging such as ultrasound/Fibroscan, and pathology assessments.
- Obtaining a more detailed history of signs and symptoms and prior or concurrent diseases.
- Obtaining a history of concomitant drug use, including nonprescription medications (e.g. acetaminophen); and herbal and dietary supplement preparations
- Exclusion of underlying liver disease
- Considering pediatric gastroenterology or hepatology consultation

All follow-up information and procedures performed must be recorded as appropriate in the CRF.

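### Worst-value, CTCAE-grade and Hy's Law tables use central laboratory results only, although Day 2 platelets and some liver repeats are run locally

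*SAP*

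**What the plan says.** SAP 2.7.3 uses central-laboratory data for every analysis of safety laboratory results and adds: "Safety laboratory data generated by local lab will only be listed". Three sets of outputs depend on a participant's extreme value:

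- shift tables to the minimum, maximum and final post-baseline value (SAP 2.5.2 and 2.7.3);
- CTCAE version 5 shift tables for the laboratory parameters of primary interest, except GLDH and direct and indirect bilirubin (SAP 2.5.2);
- counts of participants meeting the ALT and bilirubin criteria of protocol Table 16-1, with potential Hy's Law cases taken from maximum post-baseline values (SAP 2.7.3).

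The protocol sends some of the relevant tests to local laboratories:

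- **Day 2 haematology.** Footnote 4 of Table 8-1: "Hematology assessment at Day 2 should be performed locally before discharge of the patients". Section 8.4.1.1 covers haematology during the in-patient stay, "and on Day 2 prior to discharge, will be performed as per investigational site standard procedures at the local laboratory", and gives platelet monitoring as the purpose.
- **Liver repeats at 48-72 hours.** If central results will not be available, "then repeated testing should be performed at a local laboratory to monitor the safety of the participant" (10.2.1). If a liver event is later reported, "any local liver chemistry tests previously conducted that are associated with this event should have results recorded on the appropriate eCRF page".
- **Missed site visits.** "local lab collection may be used and results will be entered in the eCRF" (8.4); and "If participants cannot visit the site for protocol specified safety lab assessments, an alternative lab (local) collection site may be used" (8.4.1).

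Protocol 12.4.2 does not itself restrict laboratory summaries to central results.

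**The concern.** SAP 2.5.1 puts platelets, ALT, AST and total bilirubin among the laboratory parameters of the primary endpoints. Protocol 4.6 names hepatotoxicity and thrombocytopenia as important risks. A table of worst values is useful because it counts every threshold crossing, whoever judged it important. Here it would leave out one class of results by source, and that class includes the only scheduled platelet count between dosing and the Week 1 visit, as well as some of the repeats taken because liver tests had risen.

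What could be lost is an early platelet low, an ALT peak or higher grade, or the bilirubin part of a potential Hy's Law case. A participant whose first central ALT already exceeded 3 x ULN remains in the ALT count.

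The other outputs do not fully make up for this. The SAP 2.1.1 visit windows begin at Day 4, so Day 2 platelets are also outside every by-visit summary. Adverse-event tables take results from any laboratory, but "Abnormal laboratory values or test results constitute adverse events only if they fulfill at least one of the following criteria" (protocol 10.1.1): clinical signs or symptoms, clinical significance, or need for therapy. That route rests largely on investigator judgement.

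**Working it through.** **1. Is any table exempt from the central-only rule?** SAP 2.5.2 defines the shift and CTCAE tables without naming a laboratory. SAP 2.7.3 states the rule for all analyses and then defines the Table 16-1 counts. SAP 5.3 only refers back to 2.7.3. None of them makes an exception.

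**2. Direction.** The central values C are a subset of all values A, so max(C) ≤ max(A) and min(C) ≥ min(A). For minimum, maximum, grade and single-threshold counts, omitting recorded local values can lower a count but not raise it. One qualification concerns Hy's Law: Table 16-1 also requires no notable ALP rise above 2 x ULN, so a local ALP value could in principle take a participant out. ALP is not in the repeat panel listed in protocol 10.2.1.

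**3. The plan's own figure.** The only design figure is a 90% chance of seeing at least one event at 9% incidence (SAP Section 3, n about 24; protocol 12.8.1, n = 24-30).

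- n = 24: 1 - (1 - 0.09)^24 = 0.896, which reproduces the 90%.
- n = 30: 1 - (1 - 0.09)^30 = 0.941.

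That figure is not disputed. It shows that the study is sized on seeing a single case.

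**4. Effect of one local-only case.**

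| Denominator | Shift in the proportion |
|---|---|
| n = 30 | 1/30 = 3.3 points |
| n = 24 | 1/24 = 4.2 points |
| bracket of 10 | 1/10 = 10.0 points |
| bracket of 6 | 1/6 = 16.7 points |

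Exact (Clopper-Pearson) 95% intervals, for illustration only because the SAP plans none for these counts:

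| n | With the case counted | As tabulated |
|---|---|---|
| 24 | 1/24 = 4.2% (0.1-21.1%) | 0/24 (0-14.2%) |
| 30 | 1/30 = 3.3% (0.1-17.2%) | 0/30 (0-11.6%) |

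**5. Sensitivity to an unknown share.** Suppose a share f of participants with a qualifying extreme have it only in local results. The documents give no f, so these values are assumptions. The chance that the central-only table shows at least one case is 1 - (1 - 0.09(1 - f))^n. For f = 0.25 and n = 24 this is 1 - (1 - 0.0675)^24 = 0.813.

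| f | n = 24 | n = 30 |
|---|---|---|
| 0 | 0.896 | 0.941 |
| 0.10 | 0.868 | 0.921 |
| 0.25 | 0.813 | 0.877 |
| 0.50 | 0.669 | 0.749 |
| 0.75 | 0.421 | 0.495 |

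**The case against.** The central-only rule is an open design choice and matches the protocol's default of a central laboratory. Scheduled chemistry is central, and local liver tests are conditional repeats or contingencies. A repeat follows an elevation already seen, often centrally. With 24-30 children, listings that show multiples of ULN can be read case by case, and SAP 2.7.3 adds a full liver listing for anyone who meets an elevation criterion. Protocol Table 16-3 tells sites to record an adverse event for isolated bilirubin above 3 x ULN. Pooling laboratories mixes reference ranges, and selective recording of local liver tests could inflate counts. The haematology row of Table 8-1 is not visible in the text available for this review, so Day 2 results may be in source documents only.

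Much of this stands as a limit. Central-only data are sensible for mean changes. Local values are left out of the counts, not lost. Capture may be selective, and the Day 2 database status is unknown. None of it removes the gap:

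- A listing is not a count. The detailed liver listing is triggered by meeting a criterion, so under the central-only rule it may not pick up a participant whose only qualifying value is local.
- The Table 16-3 instruction covers neither platelets nor the 2 x ULN bilirubin component of Hy's Law.
- Protocol 8.4.1 commits the sponsor to ensuring that local results are equivalent to central ones, which weakens the argument from comparability.

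**Conclusion.** The concern holds and should be fixed. As written, the worst-value, CTCAE-grade and Table 16-1/Hy's Law tables exclude results that the protocol itself routes to local laboratories. For Day 2 platelets this affects every participant; for liver tests it affects repeats when central results are unavailable and tests when the site cannot be visited. For extremes, grades and single thresholds, the omission of valid local values can only understate. The number of cases affected cannot be derived from the documents. Each one would move a proportion by 3.3-4.2 points overall or 10-17 points within a bracket, enough to turn one case into none. This assumes that local values are valid and recorded with a usable reference range. The by-visit mean changes are not in question.

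**What to change.** Amend SAP 2.7.3 so that post-baseline local platelet and liver results held in the database with a local reference range, graded against that range, enter the minimum/maximum shift tables, the CTCAE-grade tables and the Table 16-1/Hy's Law counts. Show the central-only counts alongside, so that the effect of adding local values is visible. Keep by-visit mean changes central-only. Report how many local values could not be used because units or ranges were missing; SAP 5.1 already sends these to medical review. Confirm whether Day 2 haematology is captured in the database, since the change does nothing for values held only in source documents.

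The cost is SAP wording and some programming. Values from different laboratories would be combined as grades or multiples of ULN. Local liver values may be captured selectively, because recording is required only when a liver event is later reported. Some counts may look slightly less favourable.
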